6.9.4 Sample collection for immunologic correlative studies

All patients enrolled on this trial will have samples procured for all proposed laboratory correlative studies as summarized below. With each cycle, approximately 30-mL of blood will be collected and sent to [name]'s lab for processing. Upon receipt, each sample will be recorded and coded with a unique sample number to keep patient identification confidential. PBMCs and plasma (and/or serum) will be aliquoted and cryopreserved. The vials of viably frozen cells for all time points for each patient will be thawed at the same time whenever possible to avoid inter-experimental variability.

6.9.5 Schedule for correlative studies

Laboratory correlative studies will be obtained at screening, days 1 and 15 of the cycles and off study. Off-study correlates should be obtained at the time the patient is removed from protocol for any reason. In addition, continued T-cell correlate will be done at 1, 3, and 6 months after removal from study. Specimens obtained include BM aspirate (10-15 ml in green-top tubes using heparinized syringe) and peripheral blood (Three-10 ml green top tubes, 2 for cells and 1 for plasma).

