6.8 Patient Withdrawal

A patient should be removed from the study whenever it is necessary to safeguard his/her welfare. Occurrence of a significant adverse event or laboratory abnormalities unexpected for these patients may also necessitate discontinuation from the study. Additional reasons for removing a patient from the study are:

- Patients who participate in another investigational drug trial.
- The occurrence of unacceptable toxicity indicating the need for cessation of treatment. Patients may continue with correlative studies.
- Patient has progressive disease while receiving treatment.
- The physician feels it is in the best interest of the patient to stop treatment and the physician may determine whether to continue with correlative studies.
- Patients who express a desire to withdraw from the study (the patient has the right to withdraw for any reason without prejudice).
- Non-compliance by the patient with protocol requirements.
- Patient is lost to follow-up. If a patient does not return for scheduled visits, every effort should be made to re-establish contact. In any circumstance, every effort should be made to document patient outcome, if possible.
- Patient becomes pregnant.
- Any other reasons deemed by the principal investigator and treating physician.
- Termination of the study.

The reason for any patient withdrawal from the study should be recorded on the case report form (CRF) and the occurrence should be reported to the OSU principal investigator by email. These patients who withdraw from the study in the phase II portion of the trial will not be replaced. When a patient is removed from the study, he/she will receive treatment according to the standard of care (SOC) in the medical center and will be followed-up according to the study schedule whenever possible.

The investigator should complete all end of treatment procedures when a patient withdraws from treatment. A patient who is removed from the study by the investigator due to an adverse event (AE) or serious adverse event (SAE) will be followed until resolution of the toxicity to Grade 1 or baseline. All the tests that are required to assess the patient condition will be made as frequent as necessary until the AE or SAE has been resolved. Samples that have already been obtained will be processed.

A patient who withdraws consent before starting the study will not be followed.

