A patient who is removed from the study by the investigator since he/she did not keep the appointments will be hard to follow given the circumstances. The extreme situation of this occurrence is a patient who is defined as "lost to follow-up". Attempts to follow up on the subject will be made as long as the consent has not been withdrawn by the subject. Samples that have already been obtained will be processed.

A patient who initiated another treatment not allowed in the protocol is to be removed from the study by the investigator. Follow up will be only for safety per above. Attempts to continue the follow up of the patient by monthly phone calls or other means will be made to collect information on the patient's survival. Samples that have already been obtained will be processed.

For patients who withdraw consent, there must be clear documentation of whether the subject withdraws consents to treatment only (i.e. agrees to follow-up) or withdraws consent to treatment and follow-up.

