- h. Baseline and periodic ECGs should be performed during treatment as indicated in the flow chart. In patients who have ECG abnormalities, ECGs should be performed more routinely as clinically indicated. ECGs post-baseline should be performed as indicated
- i. Myeloma monoclonal protein assessments (Serum protein electrophoresis & immunofixation, immunoglobulin levels, serum free light chain assay) will be performed on day 1 of each cycle as well as off study.
- j. 24hr urine monoclonal protein assessment (Urine protein electrophoresis & immunofixation) will be performed at screening and as required for response assessment.
- k. Unilateral bone marrow (BM) biopsy will be done at baseline and at end of 4th cycle and evidence of progression for patients with non-secretory multiple myeloma
- l. Lenalidomide must be prescribed through and in compliance with Celgene's RevAssist® program. Prescriptions must be filled within 7 days. Any unused lenalidomide should be returned to the patient for disposition in accordance with the RevAssist® program.
- m. Dexamethasone will be started on cycle 3 only if stable disease after 2 cycles.
- n. Lenalidomide and dexamethasone will start on day 1 of each cycle. Patients will do not need to be in clinic to initiate this as all patients would have been exposed to both. Lenalidomide will be ordered for the next cycle. A pregnancy test (urine or B-HCG) will also be ordered at this time and must be negative prior to starting treatment.
- o. Laboratory correlative studies will be obtained. This will be collected through C5D1, at the off study visit, and at 1, 3, and 6 months post off-study. Off-study correlates should be obtained at the time the patient is removed from protocol for any reason.
- p. Vital signs (temperature, blood pressure, pulse rate, respiratory rate) and ECG will be closely monitored prior to, during, and after first drug infusion to avoid general infusion-related reactions. Routine vital signs with subsequent infusions, unless indicated otherwise.
- q. Correlative studies for the bone marrow aspirate will be done at screening, cycle 5 day 1, and at the off study visit.

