8.3 T-cell specific correlative science

Immunologic assessments will be performed prior to each cycle of therapy, and at 1, 3, and 6 months following the last cycle of therapy. At each time point, PBMC will be isolated from peripheral blood by ficoll density centrifugation and cryopreserved. Following completion of the study, PBMC will be thawed and 1×10^6 PBMC will be cultured with lysate generated by freeze thaw cycle of 1×10^5 unselected MM cells. As a control, PBMC will be cultured with tetanus toxoid (10 ug/ml) or media alone. Following 5 days of coculture, expression of IFN- γ by CD4(+) and CD8(+) populations will be determined by intracellular FACS analysis. Cells will be restimulated with tumor lysate for 6 h and cultured overnight with 1 ug/ml GolgiStop. The cells will be stained with CD4 or CD8 antibodies conjugated to FITC and permeabilized with Cytofix/Cytoperm plusTM. Cells will be stained with PE-conjugated anti-human IFN- γ , fixed in 2% paraformaldehyde and analyzed by flow cytometry. The effect of therapy on levels of circulating tumor reactive T cells will be determined by quantifying IFN- γ expressing CD4(+) and

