CD8(+) T cells. The impact of nivolumab and Len on tumor reactive T cells will be determined by comparing the pre-treatment levels with the peak level observed following therapy. The cytolytic capacity of tumor reactive lymphocytes will be determined by measuring expression of granzyme B and perforin in CD8(+) T cells following *ex vivo* exposure to autologous tumor lysate. The presence of naïve, memory effector, and central memory cells in the tumor reactive population will be determined by multichannel FACS analysis. The percentage of activated effector cells will be elucidated by quantifying the percentage of CD4(+)CD25(+) CD69(+) cells. Tregs will be quantified by assessing expression of FOXP3 for the CD4(+)CD25(+)CD127^{low/absent} population. When cell yields allow, we will assess the capacity of T cells to lyse autologous tumor cells in a standard chromium release assay. We will also examine the effect of nivolumab and Len on immunologic responses against previously identified tumor antigens. XBP-1, OFD-1, SOX2, MUC1, and CD138 have been identified as MM associated antigens. In HLA-A2.1 patients, we will quantify the number of CD8(+) T cells binding tetramer constructed from these antigens (as cell yields allow) at serial time points in the circulation. The persistence of tetramer(+) cells in the circulation will be determined. Functional characteristics of the tetramer positive population will be determined by measuring IFN- γ , granzyme B, IL-4, and IL-10 expression in the tetramer(+) cells by intracellular FACS staining.

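### The T-cell peak and persistence summaries have no cut-off at the start of another myeloma therapy, so effects of a next regimen can be credited to nivolumab and lenalidomide

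*Combined protocol and SAP*

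**What the plan says.** **Collection.** Section 6.9.5 plans that "continued T-cell correlate will be done at 1, 3, and 6 months after removal from study", and adds that "Off-study correlates should be obtained at the time the patient is removed from protocol for any reason". Footnote b of the calendar in 6.9.6 repeats the three late times, and footnote o says of the peripheral blood correlates: "This will be collected through C5D1, at the off study visit, and at 1, 3, and 6 months post off-study". None of these statements depends on whether new treatment has begun. Section 8.3 gives the same three times from a different anchor: "Immunologic assessments will be performed prior to each cycle of therapy, and at 1, 3, and 6 months following the last cycle of therapy".

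**Use.** Section 8.3 says the impact of the two study drugs on tumor-reactive T cells will be "determined by comparing the pre-treatment levels with the peak level observed following therapy". It then says: "The persistence of tetramer(+) cells in the circulation will be determined". Neither summary has a closing date.

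**Limits elsewhere.**
- Section 6.8 lists reasons for removal, among them "Patient has progressive disease while receiving treatment". It allows correlative studies to continue after unacceptable toxicity, and leaves them to the physician when the physician decides to stop treatment.
- Section 6.8 also says: "A patient who initiated another treatment not allowed in the protocol is to be removed from the study by the investigator". Those patients are then followed only for safety, with contacts about survival, and samples already in hand are processed.
- Sections 5.2 and 5.3 end the monthly post-treatment evaluations when new therapy begins.
- Section 7.3 censors PFS on the first day of alternative therapy.

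**The concern.** A sample drawn after a next regimen has started reflects that regimen as well as any remaining effect of nivolumab and lenalidomide. Section 6.8 sends removed patients to standard care, so a next line before the 3- or 6-month sample is foreseeable. The protocol itself treats steroids as immunologically relevant (1.5 and 7.1), so a steroid-containing next regimen could plausibly move these markers.

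The peak definition makes the point sharper, because one high late value becomes the patient's result. Persistence is exposed in the other direction: a next regimen that lowers tetramer-positive cells would look like loss of a study-drug effect. The late samples also form a larger share of the series in patients who stop early. This could colour the comparison in 7.1.1 of marker changes between responders and non-responders, if non-responders stop sooner.

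**Working it through.** The documents give no figure on this point, so there is nothing to reproduce. The check has two parts.

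**1. Which removal routes are covered?**

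| Route | Text on later T-cell samples (6.8) | New therapy before a late sample |
|---|---|---|
| Started a non-allowed treatment | Safety and survival follow-up only | Collection limited, at odds with the unconditional schedule in 6.9.5 and 6.9.6 |
| Unacceptable toxicity | Correlates may continue | Not covered if sampling continues |
| Physician's decision to stop | Physician decides on correlates | Not covered if sampling continues |
| Progression | Nothing specific; 6.9.5 applies | Not covered |

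The monthly-evaluation rule in 5.2 and 5.3 does not close the gap. It does not mention the T-cell samples, and it leaves out patients who stopped for progression. Neither 7.1.1 nor 8.3 contains an analysis rule.

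**2. How much could it matter for the peak? (illustration)**

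Inputs from the documents:
- There are three late samples, at months 1, 3 and 6.
- Counting days 1 and 15 (6.9.5) up to C5D1 (6.9.6) gives 8 post-baseline samples: C1D15, then both days of cycles 2 to 4 (6 samples), then C5D1. The off-study sample makes 9.
- Counting day 1 only, as the pre-cycle wording of 8.3 suggests, gives C2D1 to C5D1 (4) plus off-study, which is 5.
- An early stopper with 2 on-treatment samples plus off-study has 3.

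Assumptions not in the documents: samples are independent and normal with equal variance; the study drugs have no effect; a next line shifts months 3 and 6 by 1 SD in every patient.

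Let n be the number of earlier samples and δ the shift of each sample. With no shift, the share of patients whose peak is post-removal is 3/(n+3). With a shift it is the sum, over the late samples i, of ∫ φ(x−δᵢ) ∏ⱼ≠ᵢ Φ(x−δⱼ) dx. The expected peak is the mean of the distribution ∏ⱼ Φ(x−δⱼ).

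| Earlier samples n | Share, no shift | Share, months 3 and 6 at +1 SD | Increase | Expected peak, no shift → shift |
|---|---|---|---|---|
| 9 | 3/12 = 25% | 56% | 31 points | 1.63 → 1.96 SD |
| 5 | 3/8 = 37.5% | 68% | 30 points | 1.42 → 1.85 SD |
| 3 | 3/6 = 50% | 77% | 27 points | 1.27 → 1.78 SD |

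The no-shift column reflects only the number of samples; the next-line effect is the increase. At +0.5 SD and n = 5 the share is 52%.

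Downward case: with all three late samples at −1 SD and n = 9, the late samples supply the peak in about 4% of patients. The expected peak is then 1.50 SD, against 1.49 SD from the nine earlier samples alone. A lowering effect therefore hardly moves the peak and shows up in persistence instead.

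**The case against.** The strongest reply is that the protocol already restrains late sampling and that little rests on it. Section 6.8 confines patients who start a non-allowed treatment to safety and survival follow-up, and makes correlates optional on two other routes. Eligibility (3.1) requires that available beneficial therapies be exhausted, so a prompt next line cannot be presumed for everyone. The new-therapy date is already needed for PFS censoring, so late samples could be flagged at analysis. Section 7.1.1 calls the correlative work exploratory at best.

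Much of this stands, and it rules out several stronger readings that a reader might infer:
- *That late samples are always taken and never excluded.* Section 6.8 contradicts this for one route and makes sampling optional on two others.
- *That next-line effects will be credited to the study drugs.* This requires a next line before the sample, an effect on the marker, and, for the peak, that the sample be the highest. The documents give no frequency for any of these, nor for reasons for removal.
- *That every summary suffers equally.* A fixed on-treatment time such as C5D1 uses no late sample, and 8.3 plans no average over all samples.
- *That the post-removal shares of 56% to 77% measure the next-line effect.* They include the 25% to 50% that arises with no shift.

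The reply does not supply the missing rule. The limits in 6.8 concern collection on particular routes, and a date held for PFS does not by itself remove a sample from the peak or persistence summary.

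**Conclusion.** The concern holds in limited form. As written, 8.3 allows samples drawn after a next regimen to set the peak or the persistence pattern attributed to nivolumab and lenalidomide. The clearest uncovered case is the patient removed for progression; the patient removed for toxicity whose sampling continues is another.

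Under the stated assumptions, an upward shift of 1 SD at months 3 and 6 adds about 27 to 31 percentage points to the share of post-removal peaks and 0.3 to 0.5 SD to the expected peak. The shift size, its presence in every patient and the independence of samples are all assumptions, so the real effect could be much smaller.

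The consequence is confined to exploratory analyses of a listed secondary endpoint (2.4). The primary response analysis and the 18-patient decision rule are unaffected. This is a worthwhile clarification, not a threat to the trial's main conclusion.

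**What to change.** - In 8.3, limit the study-drug effect (peak) and persistence summaries to samples drawn before the start of any other anti-myeloma therapy. Show later samples separately and label them.
- Link the start date of new therapy to each post-removal sample.
- Use one anchor for the 1-, 3- and 6-month times in 6.9.5, 6.9.6 and 8.3: either removal from study or last cycle.
- Reconcile the follow-up limits in 6.8 with the unconditional sampling schedule in 6.9.5 and 6.9.6.

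The cost is a few sentences and the linking of a date already required for PFS censoring. The downside is fewer late samples in the main correlative summary, although none need be discarded.

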6.9.6 Study Calendar Schedule of Events

Investigations	Screening	C1D1 ^a	C1D15 ^a	C2D1 ^a	C2D15 ^a	CxD1 ^a	CxD15 ^a	C12D1 ^a	Off study ^b
History, physical examination, concomitant medication review	X	X		X		X		X	X
Informed written consent	X								
Confirmation of disease relapse and prior treatment	X								
Skeletal survey (CT or MRI as clinically indicated) ^c	X								X
MUGA or ECHO	X								
β-hCG ^d	X								
Toxicity evaluation	X	X		X		X	X		X
CBC / differential / platelets ^e	X	X	X	X	X	X	X ^f		X ^f
PTT, INR, TSH ^e	X								
BMP, glucose, magnesium ^e	X	X		X		X	X		
LFTs	X	X		X		X	X		
Beta 2 microglobulin ^g	X								X
12-lead ECG ^h	X								
Serum monoclonal protein assessments ⁱ	X	X ⁱ		X ⁱ		X ⁱ			X ⁱ
24hr urine for creatinine clearance	X								
24hr urine monoclonal protein and immunofixation ^j	X	X ^j		X ^j		X ^j	X		X ^j
BM biopsy, unilateral ^k	X						X ^k		X ^k
nivolumab Given		X	X	X	X	X	X	X	

Prescribe lenalidomide via RevAssist ^l	X								
Dexamethasone ^m	X								
Pregnancy test ⁿ	X								
Correlative studies, peripheral blood ^o		X ^o	X	X	X	X	X	X	X
Correlative studies, bone marrow aspirate ^q	X					X ^q			X
Monitoring ^p	X								

- a. Time points in the preceding table have a +/- 4 day window to accommodate weekends, holidays, and for patient convenience.
- b. Off study correlates will be done. In addition, continued T-cell correlate will be done at 1,3, and 6 months after removal from study
- c. Skeletal survey will be done at baseline and may be done at evidence of progression of disease. CT scan will be done to document size of plasmacytoma if this is the only measurable disease.
- d. Female patients of childbearing potential (FCBP, defined in section 8.5) must have a negative pregnancy test (β -hCG) as required by the RevAssist program.
- e. CBC d/p will be monitored biweekly in cycles 1 to 4, then monthly thereafter. Chemistry tests, including electrolytes, glucose and serum creatinine, should be performed every 2 weeks during the first 2 months of therapy and once a month thereafter. Serum electrolyte monitoring should include potassium, magnesium and calcium. PTT, INR and TSH will be checked every 2 months.
- f. Starting C5D1, CBC will be done monthly on D1 of each cycle.
- g. Beta 2 microglobulin will be done after every 2 cycles and at evidence of progression of disease.
- h. Baseline and periodic ECGs should be performed during treatment as indicated in the flow chart. In patients who have ECG abnormalities, ECGs should be performed more routinely as clinically indicated. ECGs post-baseline should be performed as indicated
- i. Myeloma monoclonal protein assessments (Serum protein electrophoresis & immunofixation, immunoglobulin levels, serum free light chain assay) will be performed on day 1 of each cycle as well as off study.
- j. 24hr urine monoclonal protein assessment (Urine protein electrophoresis & immunofixation) will be performed at screening and as required for response assessment.
- k. Unilateral bone marrow (BM) biopsy will be done at baseline and at end of 4th cycle and evidence of progression for patients with non-secretory multiple myeloma
- l. Lenalidomide must be prescribed through and in compliance with Celgene's RevAssist® program. Prescriptions must be filled within 7 days. Any unused lenalidomide should be returned to the patient for disposition in accordance with the RevAssist® program.
- m. Dexamethasone will be started on cycle 3 only if stable disease after 2 cycles.
- n. Lenalidomide and dexamethasone will start on day 1 of each cycle. Patients will do not need to be in clinic to initiate this as all patients would have been exposed to both. Lenalidomide will be ordered for the next cycle. A pregnancy test (urine or B-HCG) will also be ordered at this time and must be negative prior to starting treatment.
- o. Laboratory correlative studies will be obtained. This will be collected through C5D1, at the off study visit, and at 1, 3, and 6 months post off-study. Off-study correlates should be obtained at the time the patient is removed from protocol for any reason.
- p. Vital signs (temperature, blood pressure, pulse rate, respiratory rate) and ECG will be closely monitored prior to, during, and after first drug infusion to avoid general infusion-related reactions. Routine vital signs with subsequent infusions, unless indicated otherwise.
- q. Correlative studies for the bone marrow aspirate will be done at screening, cycle 5 day 1, and at the off study visit.

7 STATISTICAL CONSIDERATIONS

7.1 Overview of study design

This is a phase 2 trial to explore the combination of lenalidomide (without dexamethasone) and nivolumab in relapsed/refractory MM. We hypothesize that the direct anti-myeloma effect of lenalidomide in conjunction with the potential, combinatorial effect on favorable immune modulation with lenalidomide and nivolumab without deleterious effects of corticosteroid administration may improve outcomes.

7.1.1 Statistical Rationale

The purpose of the clinical trial per se is to reject the combination of lenalidomide and nivolumab from further clinical development if the therapy is insufficiently active. The trial is designed as a Sargent one-stage, three-outcome design⁴³ with the following assumptions: the inactivity cut off of the combination is 26% (the previously published, single-agent, objective response rate of lenalidomide in relapsed MM) and the activity cut off is 60% (the previously published, objective response rate of lenalidomide in combination with dexamethasone in the setting of relapsed MM). The type 1 (alpha) and type 2 (beta) error rates are both set to 5%, the probability of correctly rejecting an ineffective treatment is set to 80%. Under these assumptions, the three-outcome design specifies treatment of n=18 pts in this phase II trial. If n=7 or fewer show response to treatment, the combination will be declared ineffective. If n=10 or more pts show objective response, the treatment will be declared effective. If n=8 or 9 pts show response, the trial will be deemed inconclusive and additional pts may be enrolled.

The proportion of responses (partial and complete) will be calculated out of all eligible patients who receive any treatment in that disease group who are included in the phase II assessment. Assuming the number of responses is binomially distributed, 95% binomial confidence intervals will also be calculated for the estimate of the proportion of responses. All adverse events will be summarized by the NCI CTCAE v. 4 criteria, and tabulated across all patients who received any treatment with a focus on severe (grade 3+) adverse events and toxicities (i.e. those deemed at least possibly related to study treatment). In addition, we will summarize the proportion of patients who received dexamethasone after being stable disease but without response after 2 cycles of therapy. We will descriptively summarize how many of these patients were converted to response after the addition of dexamethasone. Since the addition of dexamethasone is part of the overall treatment regimen that is dependent on treatment outcome at a certain time point, we will not make other adjustments to the study design to evaluate these patients separately outside of this descriptive summarization of whether or not they received the dexamethasone. We will evaluate other clinical outcomes such as progression-free survival and overall survival using the methods of Kaplan-Meier, although these analyses will be exploratory and primarily to help describe the cohort itself.

Correlative analyses will also be done, including analysis of markers of the immunogenicity of nivolumab. In particular, we will evaluate biological and cellular markers in patients treated with nivolumab, measure PD-L1 expression on MM cells, percentage increase in NK cell activity, migration, immune complex formation, and cytotoxicity. Other markers such as plasma cell IHC baseline expression to characterize immunologic markers of MM cells that are responsive to nivolumab such as TNF-alpha, IFN-gamma, CD4, CD8, and granzyme B will be evaluated in addition to markers of MM cells responsive to lenalidomide (Sparc, IRF-4). Changes in these markers before and after therapy will be explored using graphical analyses as well as summarized quantitatively. We will also explore how changes in these correlative markers may differ based on whether or not the patient achieved a response or not; to accomplish this, we will utilize different plotting characters and colors for successes

vs. not in the graphical analyses to help identify potential patterns, and summarize the changes quantitatively between successes vs. not. Given the total sample size available, we expect that these analyses will be exploratory at best, but will provide important insights into mechanisms of action and vital preliminary data for future studies and hypothesis generation.

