	
Discontinuation of treatment due to disease progression will not constitute a DLT.
 
After 4 cycles of therapy or earlier if clinically indicated, response determination will be assessed by the IMWG criteria. At the end of Cycle 4, if a subject has responded (complete or partial response) or has stable disease, dosing with Nivolumab and lenalidomide will continue for a minimum of 8 additional cycles or until disease progression or withdrawal.
 
If disease progression is observed at the end of Cycle 4 evaluation, all study therapy will be discontinued. Confirmation of progression of disease will be done according to the IMWG criteria.
 
Following the 30-day post-treatment follow-up assessment, additional evaluations will occur once per month (unless subject discontinued due to progression) until the earliest of the following events: disease progression, the time of initiation of new therapy, death or study completion.
 
Study completion is defined as 30 days after the last subject remaining on study medication discontinues study medication.
 
An independent Data Monitoring Committee will continue oversight of this trial.
 
Treatment will continue until Progression of disease, death, unacceptable toxicity or patient or treating physician decision to discontinue therapy.

Dosing Regimen	Nivolumab will be given at a dose of 240 mg every 2 wks (Day 1 and 15) of a 28-day cycle. Lenalidomide will be given at starting dose of 25 mg days 1-21 of a 28 day cycle. Dexamethasone can be added after 2 cycles if stable disease.
Planned Sample size	18 patients will be recruited
Duration of Study Period	
Patient will continue study treatment at the treating physician's discretion. Patients achieving at least a stable disease can continue treatment until progression of disease, death, unacceptable toxicity, or patient decision. Overall response will be assessed after 4, 8, and 12 cycles.
 
The total study enrollment period is expected to be up to 12-18 months.

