5.4 Study Accrual

Eighteen patients will be accrued.

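### The 7-of-18 futility boundary gives an exact type 2 error of 5.8%, slightly above the stated 5%; at n=18 only a boundary of 6 meets every stated limit

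*Combined protocol and SAP*

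**What the plan says.** Section 7.1.1 states: "The trial is designed as a Sargent one-stage, three-outcome design". The inactivity cut-off is 26%, from published single-agent lenalidomide, and the activity cut-off is 60%, from published lenalidomide plus dexamethasone. On the error rates it says "The type 1 (alpha) and type 2 (beta) error rates are both set to 5"%, and "the probability of correctly rejecting an ineffective treatment is set to 80"%.

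The section presents the sample size and boundaries as following from these inputs: 18 treated patients, with three outcomes.

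- 7 or fewer responses: "If n=7 or fewer show response to treatment, the combination will be declared ineffective".
- 8 or 9 responses: "If n=8 or 9 pts show response, the trial will be deemed inconclusive and additional pts may be enrolled".
- 10 or more responses: effective.

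The same section later plans confidence intervals for the response proportion: "Assuming the number of responses is binomially distributed". The sample size is repeated in the synopsis ("18 patients will be recruited") and in Section 5.4 ("Eighteen patients will be accrued"). Neither the method used to find the boundaries nor the error rates they attain is given.

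**The concern.** This is the trial's only efficacy decision rule, and Section 7.1.1 gives its purpose as stopping development of a combination that is not active enough. The lower boundary is therefore the one that matters most. If it does not deliver the stated beta, the plan reports an error rate that its own rule does not have, and the fault lies in the risk of discarding an active regimen.

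A second point follows from the missing attained figures. Nobody can see from the plan that alpha and correct rejection are far better than their limits, or how often a truly 60% regimen would fail to be declared effective.

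**Working it through.** **Inputs**, all from Section 7.1.1: n = 18; p0 = 0.26; p1 = 0.60; ineffective if X ≤ 7; effective if X ≥ 10; limits alpha ≤ 5%, beta ≤ 5%, correct rejection ≥ 80%. X is taken as binomial(n, p), and alpha as one-sided, which the form of the rule implies.

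**Formulas**
- alpha = P(X ≥ 10 | p0)
- beta = P(X ≤ 7 | p1)
- correct rejection = P(X ≤ 7 | p0)
- declared effective when active = P(X ≥ 10 | p1)
- inconclusive = P(X = 8 or 9 | p)

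**The plan's rule at n = 18**

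| Quantity | Stated limit | Exact binomial |
|---|---|---|
| alpha | 5% | 0.73% |
| beta | 5% | **5.76%** |
| correct rejection | at least 80% | 93.01% |
| declared effective at 60% | none | 73.7% |
| inconclusive at 26% | none | 6.3% |
| inconclusive at 60% | none | 20.6% |

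Beta exceeds its limit by 5.76 − 5.00 = 0.76 points. Nothing else breaches a stated limit; in particular, the boundary of 10 does not.

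**Every candidate lower boundary near 7, n = 18**

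| Ineffective if | beta (60%) | correct rejection (26%) | Meets both limits? |
|---|---|---|---|
| ≤ 5 | 0.58% | 68.2% | No: below 80% |
| ≤ 6 | 2.03% | 83.7% | Yes |
| ≤ 7 | 5.76% | 93.0% | No: beta above 5% |
| ≤ 8 | 13.5% | – | No: beta above 5% |

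Beta rises and correct rejection never falls as the boundary moves up, so ≤ 6 is the only one that works at n = 18.

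**What the choice between 6 and 7 affects.** Only exactly 7 of 18 (38.9%) changes verdict. Its probability is 3.74% at a true 60% (5.76 − 2.03, up to rounding) and 9.31% at a true 26% (93.01 − 83.70).

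**Where the boundary may have come from.** A normal approximation has mean 18 × 0.60 = 10.8 and standard deviation √(18 × 0.60 × 0.40) = 2.078.
- Without continuity correction: z = (7 − 10.8)/2.078 = −1.83, so beta is 3.4%.
- With it: z = (7.5 − 10.8)/2.078 = −1.59, so beta is 5.6%.

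An uncorrected approximation could thus explain the choice of 7, but the plan does not say that one was used.

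**Sensitivity to the 60%.** Exact beta for ≤ 7 of 18 is 5.56% at p1 = 60.2% and 4.80% at 61%. It falls to 5% only when p1 reaches 60.8%.

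**One more patient.** Keeping ≤ 7 and ≥ 10 with n = 19 gives alpha 1.2%, beta 3.5%, correct rejection 90.6%, declared effective at 60% 81.4%, and inconclusive 8.2% (at 26%) and 15.1% (at 60%).

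**The case against.** The best reply is that the excess is smaller than the uncertainty in the 60% itself. Table 1-1 (Section 1.3.1) reports 108/177 = 61.0% and 106/176 = 60.2% for lenalidomide plus dexamethasone. Exact beta for the current boundary is 4.8% at 61.0%, 5.5% at 106/176, and 5.2% at the pooled 214/353 = 60.6%. One of the two source trials therefore puts the rule inside its limit. It can be added that the plan names no method for the boundaries, since the binomial sentence introduces the confidence intervals, and that an uncorrected normal approximation gives 3.4%.

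The choice of 7 can also be defended on its merits. Seven of 18 is about 2.5 times as likely at 26% as at 60% (9.3/3.7), so calling it ineffective serves a trial meant to reject inactive treatment. Moving to 6 costs 9.3 points of correct rejection to gain 3.7 points of beta.

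Much of this stands as a reason to call the matter small and to leave the choice of boundary with the sponsor. It does not remove the mismatch. The plan commits to 60%, not 61%; the pooled rate still gives more than 5%; and only the approximation without continuity correction falls below the limit. The low chance of declaring a 60% regimen effective, 73.7%, breaches nothing, because no target is set for it. It is an omission from the report of the design, not an error in it.

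**Conclusion.** The concern holds. With the plan's own inputs and an exact binomial calculation, the stated rule has a type 2 error of 5.8% against a stated 5%, while alpha and correct rejection are comfortably within their limits. The discrepancy is minor in size but real, and a compliant boundary exists at the same sample size. It should be corrected because it concerns the primary decision rule and the correction is almost free.

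The conclusion rests on reading the three error figures as limits, on p1 = 60% exactly, and on 18 patients in the response denominator.

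**What to change.** Name the exact binomial method in Section 7.1.1 and take one of these routes. If response data have already been reviewed, only the first is open.

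1. **Keep the rule and state what it delivers**: alpha 0.7%, beta 5.8%, correct rejection 93.0%, declared effective at 60% 73.7%, inconclusive 20.6% at 60% (6.3% at 26%). Cost: one sentence.
2. **Keep n = 18 and lower only the futility boundary**: 6 or fewer ineffective, 7 to 9 inconclusive, 10 or more effective. All stated limits are met (alpha 0.7%, beta 2.0%, correct rejection 83.7%). Cost: two numbers in 7.1.1 and no extra patients by design. The price is that inconclusive results rise from 6.3% to 15.6% at 26% and from 20.6% to 24.3% at 60%, in a zone where more patients may be enrolled.
3. **Keep both boundaries and treat 19 patients**, which also meets all stated limits. Cost: one patient, and the sample size changed in the synopsis, 5.4 and 7.1.1. The gain disappears if one of the 19 falls out of the denominator (eligible and treated), which returns the rule to 18 patients.

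As a separate design choice, not a correction, option 2 could be paired with an effective boundary of 9 (alpha 2.5%, declared effective at 60% 86.5%), still within the stated limits.
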